Supporting and Enhancing NICU Sensory Experiences (SENSE)
NCT number: 03316547
Document date: 4-20-2021

This study was registered on clinicaltrials.gov prior to enrollment under trial #201601057. This study was approved by the Washington University Human Research Protection Office with a Ceded Review at the University of Southern California. Parents signed informed consent.

Participants and study site. Seventy parent-infant dyads of very preterm infants born \leq 32 weeks estimated gestational age (EGA) were recruited within the first week of life from consecutive admissions at St. Louis Children's Hospital NICU, an 85-bed (that expanded to 132-bed during the course of the study) level IV NICU from August 2017 to June 2018. Infants were excluded if they had a suspected or confirmed congenital anomaly, were assigned to the NICU's open ward (rather than a private room), or had parents who did not speak English. They were withdrawn if they became wards of the state or were transferred to a different NICU prior to discharge home.

Power. We defined primary outcome variables for each time point (at term equivalent age and one-year corrected age) and did a power analysis, to estimate sample size, incorporating both. The primary outcome variable at term equivalent age (35-41 weeks PMA) was the Excitability subscale score on the NICU Network Neurobehavioral Scale (NNNS). Excitability is a combination of both motor and behavioral responses, and previous work in our lab has demonstrated it to be a good predictor of later motor, cognitive and language outcomes. We estimated the variance of the Excitability subscore using data from preterm infants born $<$ 30 weeks gestation enrolled in a longitudinal cohort from 2007-2010 and evaluated with the NNNS at term age. For this trial, a total sample of $n=46$ (23 in each group) will provide 80% power when the true NNNS group difference is 2.2 (2-sided test with $\alpha=0.05$). In a sample of typical full-term infants, the Excitability subscale score has a mean of 4.3 and a standard deviation of 2.4. A group difference of 2.2 would be a difference of almost 1 standard deviation. Our primary outcome variable at one-year corrected age was the Ages and Stages

Questionnaire (ASQ) Communication score. This was chosen as our primary outcome of interest, due to previous findings of poorer language outcomes in preterm infants hospitalized in low stimulation environments with poor parent engagement. The variance of the Communication score was estimated using a sample of preterm infants enrolled in our lab in 2011 who received the ASQ at age 3 years. A sample of $n=46$ provides 80% power when the true group mean ASQ difference is 9.5 (2-sided test with $\alpha=0.05$). In a normative sample, the Communication score on the ASQ has a mean of 52.9 with a standard deviation of 11.1. A total sample of $n=46$ (23 in each group) would be a large enough sample to detect a difference of less than 1 standard deviation across groups at the one-year follow-up assessment. Seventy infants were enrolled to account for 15% attrition during the course of the NICU hospitalization (for $n=60$ at term age) and another 20% attrition by the one-year follow-up assessment ($n=48$ at one-year of age).

Overview of procedures. Parent-infant dyads, enrolled within 7 days of birth, were randomized to either the standard-of-care group or SENSE multisensory program group. The randomization scheme was stratified on level of immaturity (≤ 28 weeks EGA or > 28 weeks EGA) and was uploaded to REDCap prior to study initiation. The biostatistician, who was not involved in other study procedures, established the randomization allocation sequence. Various members of the research team (research coordinator, principal investigator, neonatal therapist) enrolled families, pulling a sealed envelope that disclosed the group assignment after enrollment. Parents with infants in the SENSE group were provided with SENSE program education and daily support by a neonatal therapist to engage in the SENSE program (described below) in addition to receiving standard-of-care. Sensory exposures were tracked on bedside logs that contained sensory exposure dose targets for each day. The monitored standard-of-care

group received standard NICU care at the study site (described below) and tracked sensory exposures on bedside logs.

Standardized measures of maternal mental health and infant development were contained in a questionnaire that was completed by mothers at 35-41 weeks PMA in the NICU and at one-year corrected age. The questionnaire has been used in our longitudinal studies of preterm infants since 2007 and takes approximately 30 minutes to complete.

Standard-of-care. At the time of this study, much like other contemporary NICUs, parents were allowed to be present in the NICU 24 hours per day, with significant variability in the amount, types and timing of actual parent engagement. Infant holding was supported, provided the infant could maintain physiological and temperature stability. Infants were held while on mechanical ventilation, but holding was not encouraged when infants were on oscillatory ventilation and/or when chest tubes were in place. Nurses and therapists fostered parent participation through instruction on caregiving and developmentally appropriate interactions, but these were balanced with other priorities of medical care. No specific amount of positive sensory exposures was targeted, and practices varied based on the comfort level of nurses, the medical team, and the parents. Suboptimal parent presence, holding, and language exposure have previously been reported at the study site. The study site is consistent with other hospitals, where there is significant variation in use of sensory based interventions and decreased parental involvement. The SENSE program addresses the current lack of a national standard for positive sensory exposures and the resultant inconsistency of application of these exposures across hospitalization.

SENSE multisensory program. The SENSE program includes the provision of specific types and amounts of evidence-based tactile, auditory, visual, vestibular/kinesthetic, and olfactory interventions to be conducted by parents with their preterm infants, with a specific amount defined for each day of hospitalization (see Appendix 1). The program changes across PMA, and a sensory support team fills in the gaps when parents are not available. The education and parent guidance that is part of the SENSE program was overseen by a neonatal therapist (with the study using a neonatal occupational therapist and physical therapist).

SENSE program education. Parents randomized to the SENSE group received an educational booklet for the SENSE program which informed them about the premise of the multisensory interventions, along with identified targets in the amounts of daily multisensory exposures that are tailored to each infant's PMA. Parents could choose to provide one sensory exposure at a time or could provide multisensory interventions, based on the infant's tolerance. Parents were able to choose different types of each sensory exposure from options that have evidence to support their use and are appropriate at each PMA. The parents and medical team also opted for exposures within an infant's range of tolerance (such as using gentle human touch for an infant too sick to be transferred out of the bed to be held). Parents also received verbal education by the neonatal therapist on the research team within one week of enrollment and at least weekly thereafter to reinforce content in the booklet.

The sensory support team. When the parents or family members were unable to reach the target doses as defined in the SENSE program, a member of the sensory support team was assigned to deliver appropriate multisensory interventions. The sensory support team consisted of trained volunteers who provided gentle human touch and language exposure to medically stable infants as directed by the research team.

Modifications to the sensory intervention based on infant factors. The SENSE program is tailored to be responsive to each infant's cues when receiving the stimuli as

well as individualized based on concurrent medical issues. The neonatal therapist on the study team assessed the infant's tolerance each week, or more often if needed, and adjusted the multisensory interventions accordingly when not tolerated. The infant assessment used for the SENSE program is part of the manualized intervention and consists of infant observations, evaluation, and collaboration with the medical team. Any modifications to the structured dose and timing of the multisensory interventions were communicated to the parents, medical team, and sensory support team and documented by the research team.

Treatment fidelity/documenting sensory exposures. To assess treatment fidelity and to ensure treatment differentiation, sensory exposures (conducted by parents, the medical team, or the sensory support team) were captured on bedside logs for both groups. To ensure *treatment integrity*, we measured whether the daily doses defined in the SENSE program were being met each day, with specific attention to auditory and tactile exposures, which have large dose targets and are measurable by amount of time. Continuous review of sensory exposures during the course of the study also enabled activation of the sensory support team as needed. Differences in sensory exposure in the SENSE and standard-of-care groups are reported in a previous publication.

Masking participants and blinding evaluators. Parents were enrolled in this study, understanding that they would be assigned to one of two types of sensory approaches. They were masked from whether they were in the treatment group (SENSE program) or control group (standard-of-care), and the details of what we wanted them to do (within their assigned approach) were not communicated until after enrollment. All assessments in the NICU were conducted at the infant's bedside by a certified and trained evaluator, who was blinded to treatment assignment (as well as study details).

Medical factors. Medical factors were collected from both groups using the EPIC electronic medical record to define the characteristics of the sample and enable statistical control of other factors that can impact outcome. From these factors, a medical risk score was defined as the infant having any of these factors during the NICU hospitalization: inotropic support, patent ductus arteriosus (PDA), necrotizing enterocolitis (NEC), parenteral nutrition > 21 days, mechanical ventilation > 7 days, bronchopulmonary dysplasia, or cerebral injury (grade III or IV intraventricular hemorrhage or cystic leukomalacia) due to evidence associating them with adverse neurodevelopmental outcome .

Social factors. Social factors were collected from EPIC as well as from the parent questionnaire. A social risk score, used in parallel research studies and modified for this study, was used to assess family environment after NICU discharge.

Outcomes at term equivalent age, prior to NICU discharge.

NICU Network Neurobehavioral Scale (NNNS). Between 35-41 weeks PMA, infants were assessed at bedside with the NNNS by a trained and certified evaluator blinded to treatment group. The NNNS has been used extensively with preterm infants, and has acceptable internal consistency ($\alpha = 0.87-0.90$), good test-retest reliability ($\alpha = 0.30-0.44$), and predictive validity with relationships to Bayley-II mental ($p=0.011$, $R^2=0.295$) and psychomotor ($p=0.002$, $R^2=0.441$) scores. It has also been shown to relate to ASQ scores at age 3 years. Habituation was not assessed, but the remaining 12 summary scores were used as outcomes.

Hammersmith Neonatal Neurological Evaluation. Between 35-41 weeks PMA infants were also assessed with the Hammersmith Neonatal Neurological Evaluation (HNNE). It has excellent clinical utility as a quick assessment of neonatal neurological status with acceptable content and criterion validity. The interrater reliability of the assessment is

good for both optimality scores and subtotal scores (ICC > 0.74 and ICC 0.6-0.74 respectively). The total score was used as an outcome variable.

Sensory processing. The questionnaire included the Sensory Profile 2 (short form). It is used in clinical practice and research and has good test-retest reliability ($\alpha=0.81-0.90$), validity, and internal consistency ($\alpha=0.83$). Summary scores for Tactile Sensitivity, Taste/Smell Sensitivity, Movement Sensitivity, Auditory Filtering, Under Responsiveness/Seeks Sensation, Low Energy/Weak, and Visual/Auditory Sensitivity were used as outcomes.

Maternal mental health outcome. The questionnaire included the State Trait Anxiety Inventory (STAI), the Edinburgh Postnatal Depression Scale (EPDS), the Life Stress Subscale of the Parenting Stress Index (PSI), the Perinatal Post-Traumatic Stress Disorder Questionnaire (PPQ), the Parental Stressor Scale: NICU (PSS-NICU), the Maternal Confidence Questionnaire (MCQ), and the Infant Characteristics Questionnaire (ICQ). The STAI is the most widely used self-report assessment of anxiety in adults. Internal consistency coefficients range from 0.86-0.95, and test-retest reliability ranges from 0.65-0.89. The STAI has good construct and concurrent validity. The EPDS measures and has cut-offs for diagnosis of clinical depression. The EPDS has fair validity (specificity of 49-100%, sensitivity of 65%-100%, 83% predictive value). The scale has good test retest reliability of 0.92, split half reliability of 0.88 with a standardized α coefficient of 0.87. The PSI (4th ed) screens for stress in the parent-child relationship and has good reliability, internal consistency with $\alpha=0.96$, and is useful across diverse populations. The PPQ is a measure of post-traumatic stress symptoms in the perinatal population and has good internal consistency (coefficient $\alpha=0.85$) and test-retest reliability ($r=0.92$). The PSS NICU measures parental perception of stressors arising from the physical and psychosocial environment of the NICU and has acceptable internal consistency (Cronbach's $\alpha > 0.7$ for all scales) and good construct validity across all scales ($r=0.45$, $p < 0.05$). The MCQ measures maternal confidence in

parenting and has fair test-retest reliability (0.69) and good internal consistency with Cronbach's alpha between 0.86 to 0.93. The ICQ measures perceptions about ability and competence in providing infant care and has good internal consistency (Cronbach's alpha from 0.39 to 0.79) and test-retest reliability (Pearson's r between 0.47-0.70).

Outcomes at one-year corrected age.

Developmental outcome. At one-year corrected age, the parents completed the ASQ, a parent-report measure of developmental outcome, which can be used for children from 2 months to 5 years. Scores were obtained for: Communication, Gross Motor, Fine Motor, Problem Solving, and Personal-Social. The ASQ has good validity (combined validity 86%, 73%-100%) and reliability (test-retest reliability $\alpha = 0.75-0.82$, interrater reliability $\alpha = 0.43-0.69$).

Sensory processing: Sensory processing was also measured at one-year corrected age using the Sensory Profile-2 (short form).

Maternal mental health. The STAI, PSI, modified PPQ, ICQ, and MCQ were also administered at 1-year corrected age. While the EPDS was used to determine maternal depression at term age, the Beck Depression Inventory II (BDI-II) was used to determine maternal depression at 1 year corrected age. The BDI-II has good validity, internal consistency with Cronbach's α coefficient 0.83 to 0.96 and good reliability (test retest $r = 0.73$ to 0.96).

Feeding outcomes at one-year of age. Feeding was assessed with the Pediatric Eating Assessment Tool (PediEat) and the Behavioral Pediatric Feeding Assessment Scale (BPFAS). The PediEAT measures symptoms of feeding problems in infants and children aged 6 months to 7 years. It has excellent internal consistency with Cronbach's α coefficient 0.83 to 0.92, good to excellent test-retest reliability (ICC=0.95), and established construct validity. The BPFAS defines patterns of mealtime and feeding

behaviors in young children aged 9 months to 7 years. It has good test-retest reliability (ICC=0.91), internal consistency with Cronbach's α coefficient 0.71 to 0.81, and established content and concurrent validity.

Statistical analysis.

Descriptive statistics were used to report characteristics of the sample. Differences in medical and sociodemographic factors across groups were explored using independent samples t-tests, chi-square analyses, regression models, and nonparametrics. All factors that were different across groups ($p < 0.05$ and $r > 0.30$) were considered for inclusion in the statistical model as a covariate, as long as they were not already represented in the social risk or medical risk scores.

First, mixed random effects models were used to investigate group differences in NNNS, ASQ, and other outcomes. Correlation between siblings, who are multiples, were modeled by using mother-infant dyad as a random effect. PMA at the time of assessment was controlled for due to its previously reported relation to neurobehavioral outcome. To further explore group differences, a second analysis was conducted, controlling for baseline covariates of social risk score and medical risk score. In addition, a final analysis was conducted to understand the potential impact of parent-driven, compared to sensory support driven, sensory interventions. An interaction between parent engagement (50% of interventions done by the parents) and treatment group was investigated in a factorial model. Other analyses of outcomes included mixed effects repeated measures ANOVA for continuous measures across time and using logistic regression for categorical outcomes of measures conducted at one point in time. The threshold of significance was $p = 0.05$.

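### Parents are described as masked to group, but SENSE parents could not be, and parents rate the one-year primary outcome (ASQ Communication)

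*Combined protocol and SAP*

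**What the plan says.** The section headed Masking participants and blinding evaluators makes three statements about parents in the Combined protocol and SAP. They enrolled "understanding that they would be assigned to one of two types of sensory approaches". Next: "They were masked from whether they were in the treatment group (SENSE program) or control group (standard-of-care"). Last, the details of what was asked of them within their assigned approach "were not communicated until after enrollment". The same section says that the evaluator of the NICU assessments was blinded. The documents state no other blinding of a rater.

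Other sections describe what happened after enrollment:

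- Overview of procedures: "Parents with infants in the SENSE group were provided with SENSE program education and daily support by a neonatal therapist".
- The section on SENSE program education states: "Parents randomized to the SENSE group received an educational booklet for the SENSE program which informed them about the premise of the multisensory interventions". According to the same section, the booklet also set daily exposure targets by PMA. A later sentence there adds: "Parents also received verbal education by the neonatal therapist on the research team within one week of enrollment and at least weekly thereafter".
- Standard-of-care: the control arm had no target amount of exposure. Control families also kept bedside logs.

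On the one-year outcome, the Developmental outcome section says: "At one-year corrected age, the parents completed the ASQ, a parent-report measure of developmental outcome". The Power section names the ASQ Communication score as the primary outcome at that age.

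**The concern.** The masking statement describes a property that the intervention, as the plan itself sets it out, does not allow in the SENSE arm. A parent who holds a booklet named after the program, works to its daily targets and is coached on its premise knows which group the child is in.

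This bears on a primary outcome because participant and rater are the same person at one year. Parents who spent the NICU stay delivering a program meant to help development may answer developmental questions differently from parents who did not. Any such difference adds directly to the estimated group difference. The statistical model cannot separate it from a treatment effect. The Sensory Profile-2 and the maternal mental-health scales are also completed by the mother and share the problem. A reader who takes the masking sentence at face value would discount this source of bias.

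**Working it through.** **Step 1. Set the sections side by side.**

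| Question | SENSE arm | Standard-of-care arm |
|---|---|---|
| Named booklet giving the premise | Yes | Not described |
| Daily exposure targets | Yes | No target amount |
| Study therapist | Daily support, verbal education at least weekly | Usual NICU staff instruction only |
| Bedside log | Yes | Yes |
| Details withheld | Until after enrollment | Until after enrollment |
| Rater of one-year ASQ | Parent | Parent |

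SENSE parents know the care they give and its name, so masking to group fails in that arm. For control parents the only certain facts are usual care and a log, so their awareness is undetermined.

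**Step 2. Reproduce the plan's sample size.** Inputs from the Power section: difference 9.5, two-sided alpha 0.05, power 80%, 23 per group. The planning SD is not given, so the stated normative SD of 11.1 stands in for it.

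- Normal formula: n per arm = 2 × (SD/difference)² × (1.960 + 0.842)² = 2 × (11.1/9.5)² × 7.85 = 21.4, rounded up to 22.
- Noncentral t: power at 23 per arm is 0.810, and 23 is the smallest number per arm that reaches 80%.

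The stated 46 in total is reproduced. The masking point does not change it.

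**Step 3. Illustrate what a reporting shift would do.** The documents give no figure for reporting bias. Both the shift b and its direction (favouring SENSE) are assumptions.

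- Standard error = 11.1 × √(2/23) = 3.27 points.
- Critical t on 44 degrees of freedom = 2.015, so the smallest significant difference is 2.015 × 3.27 = 6.6 points.
- With no true effect, the test statistic follows a noncentral t with noncentrality b/3.27. The false-positive rate is the probability that it exceeds 2.015 in absolute value.

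| Assumed shift b (points) | b/11.1 (SD) | Noncentrality | Two-sided rejection rate |
|---|---|---|---|
| 0 | 0 | 0 | 5.0% |
| 2 | 0.18 | 0.61 | 9.2% |
| 3 | 0.27 | 0.92 | 14.6% |
| 4 | 0.36 | 1.22 | 22.3% |
| 5 | 0.45 | 1.53 | 32.1% |

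With 24 per arm (the 48 expected at one year) the last four rates are 9.4%, 15.0%, 23.1% and 33.3%.

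**Step 4. Turn it round as a tipping point.** If the observed difference equalled the planned 9.5 points with this standard error, a shift of 9.5 − 6.6 = 2.9 points would be enough to remove significance.

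Steps 3 and 4 use a simple two-sample comparison, not the planned mixed model with a random effect for the dyad and adjustment for PMA at assessment.

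**The case against.** The strongest defence is that the masking sentence was meant more narrowly. Parents were told of two sensory approaches, both arms kept logs, and parents may not have been told which approach was experimental. Consent pages are not in the file, so this cannot be ruled out. It may well hold for control parents. It does not rescue the wording, because the text claims masking to group. Withholding the hypothesis is a different property, and in the SENSE arm a booklet that sets out the premise weakens even that.

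A reader might infer that the plan presents the ASQ as a masked outcome. It does not. It openly calls the ASQ a parent report, and its claim of evaluator blinding is confined to the NICU assessments. The inference arises only because the raters are said to be masked.

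A reader might also draw too sharp a contrast between the arms. The sensory support team worked with infants to fill gaps when families could not reach the targets, so it is not evidence that every SENSE parent was visited. Usual care also included staff instruction on caregiving and developmentally appropriate interaction.

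Two further objections stand. First, nothing shows that a reporting shift occurred, and coached parents could rate more critically. Second, a parent-delivered program cannot be hidden from the parents who deliver it, and mothers' mental health is measured here by self-report. Open delivery is therefore not a fault in the design. The fault lies in describing it as masking.

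**Conclusion.** The point holds for the SENSE arm: the statement that parents were masked to group is contradicted by the plan's own account of the intervention. For control parents the documents do not settle it. The consequence is that the one-year primary outcome and the other parent-completed outcomes have no masked rater. The plan describes no masking check, no independent one-year developmental assessment and no sensitivity analysis for reporting bias.

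The size is conditional. An assumed shift of 2 to 5 points in favour of SENSE would raise the false-positive rate from 5% to between about 9% and 32%, given 23 per arm, SD 11.1 and a two-sample t-test. These figures show how sensitive the result would be; they are not an estimate of bias in this trial. The documents do not support a conclusion that the one-year result is biased, nor one that the trial is invalid. NNNS Excitability, the term-age primary outcome, is unaffected. The point should be acted on because it governs how one of two primary outcomes may be read.

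**What to change.** 1. Replace the parent-masking statement with: evaluator-blinded for NICU assessments (NNNS, HNNE); parents were aware of their assigned approach. State for each arm what was withheld from parents and until when.
2. Label the ASQ, the Sensory Profile-2, the maternal scales and any other parent-completed measure as unmasked parent report. The feeding section does not name the respondent for its two scales; say who completed them and label them accordingly.
3. Limit blinded-efficacy conclusions to the term-age NNNS and HNNE. These do not measure communication at one year, so no blinded conclusion is available for that outcome.
4. Report the ASQ shift that would remove significance: the absolute estimated difference minus the critical value times its standard error, both taken from the fitted mixed model.

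A question asking parents which approach they thought was being tested is no longer possible. Recruitment ended in June 2018, and the document, dated April 2021, reports the one-year questionnaires as completed.

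The cost is some rewording and one small table, with no new data. The downside is a weaker claim for the one-year result.

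### Randomisation is stratified by gestational age, but no listed model includes the stratum; extra covariates are chosen by how far the arms happen to differ

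*Combined protocol and SAP*

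**What the plan says.** Under Overview of procedures: "The randomization scheme was stratified on level of immaturity", with the cut at 28 weeks EGA. Dyads are enrolled within 7 days of birth. Blocking within strata is not mentioned.

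Under Statistical analysis, the models are:

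- First model: group, with "PMA at the time of assessment was controlled for due to its previously reported relation to neurobehavioral outcome". Correlation between multiples is "modeled by using mother-infant dyad as a random effect".
- Second model: "controlling for baseline covariates of social risk score and medical risk score".
- Final model: a parent engagement by group interaction.
- Repeated-measures ANOVA and logistic regression are also named, without covariates.

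None of these names EGA or the stratum.

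Further covariates enter through a screen: "All factors that were different across groups ($p < 0.05$ and $r > 0.30$) were considered for inclusion", unless the social or medical risk score already represents them. The text does not say what r is correlated with, or which of the models the screen feeds.

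Under Medical factors: "a medical risk score was defined as the infant having any of these factors during the NICU hospitalization". The components include parenteral nutrition beyond 21 days and ventilation beyond 7 days. EGA is not a component.

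**The concern.** A variable used to stratify randomisation is normally kept in the analysis, for two reasons. If it predicts outcome, a model term removes its variance from the error and raises power. If allocation is balanced within strata, a test that ignores the stratum uses a standard error that is too large and so rejects too seldom.

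The terms the plan does list are not substitutes. PMA at assessment (35–41 weeks) is a different variable, measured after randomisation. The medical risk score is called a baseline covariate, but it covers the whole NICU stay, so at least its 21-day and 7-day components cannot be complete at an enrolment within 7 days of birth. It also enters only from the second model. The social risk score is described as reflecting the family environment after discharge.

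The screen does not repair this. It selects on imbalance and not on prognostic value, and stratification works against imbalance in EGA. Passing leads only to being considered, so the adjustment set behind the reported treatment estimate is open.

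**Working it through.** **Inputs from the Power section.** n = 46 (23 per arm) gives 80% power, two-sided α = 0.05, for an NNNS Excitability difference of 2.2 or an ASQ Communication difference of 9.5. Seventy infants are enrolled, with 15% and then 20% attrition: 70 × 0.85 = 59.5 (about 60) and 60 × 0.80 = 48.

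**The plan's own figure.** The planning SDs are not stated, so n = 46 cannot be strictly reproduced. A two-sample t-test with 23 per arm has 80% power at a standardised difference d = 0.845. The implied SDs are 9.5/0.845 = 11.2 for the ASQ (normative 11.1) and 2.2/0.845 = 2.6 for the NNNS (normative 2.4). Both are plausible; d = 0.845 is used below.

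**Assumption.** R² is the share of within-arm outcome variance explained by the stratum. The documents do not give it, so 0–30% is shown.

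**Closed form under exact balance.** The true variance of the group difference is proportional to 1 − R², but a test omitting the stratum estimates it as if proportional to 1. Its real type I error is about 2[1 − Φ(1.96/√(1 − R²))]. At R² 10%, 1.96/√0.90 = 2.066, giving 3.9%; at 5, 20 and 30% it is 4.4, 2.8 and 1.9%. With the stratum included, the noncentrality at n = 48 is 0.845 × √12/√(1 − R²) on 45 degrees of freedom. Power is 81.7, 83.6, 85.5, 89.3 and 92.8% at R² 0, 5, 10, 20 and 30%.

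**Simulation of more realistic allocation.** Least squares with and without the stratum, two equal strata, 120,000 trials per cell. The power and first type I columns take allocation balanced at 70 with random loss to 48.

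| R² | Power, stratum omitted | Power, stratum included | Type I error, omitted (70 to 48) | Type I error, omitted (exact balance, n = 60) |
|---|---|---|---|---|
| 0% | 81.4% | 81.1% | – | – |
| 5% | 82.0% | 83.2% | 4.6% | 4.3% |
| 10% | 82.0% | 85.0% | 4.3% | 3.9% |
| 20% | 83.0% | 89.1% | 3.5% | 2.9% |
| 30% | 83.8% | 92.5% | 2.8% | 1.9% |

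With simple randomisation within strata, type I error with the stratum omitted is 4.9–5.1% throughout, so the conservatism depends on balance. Across exact balance, attrition and simple randomisation, adding the stratum changes power by 0 to −1 point at R² 0, then by about +1, +3, +5 to 7 and +7 to 11 points at 5, 10, 20 and 30%. Power with the stratum omitted never falls below 80%. A 30/70 split of strata gives similar gains (1.3, 2.8, 5.9 and 8.9 points, 70 to 48).

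**Which R² is realistic for the NNNS.** The plan quotes test-retest reliability of 0.30–0.44. If that is the share of score variance that is stable, an R² of 20% would need the stratum to explain 0.20/0.44 = 45% to 0.20/0.30 = 67% of the stable part. The 0–10% rows are the relevant ones.

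**The screen, if r is the correlation with arm.** At n = 70, r = 0.30 gives t = 0.30 × √(68/0.91) = 2.59, p = 0.0116. The p < 0.05 condition alone needs only r of 0.235, so r > 0.30 is what binds. A pure-chance factor passes with probability 1.2%. At least one of k independent factors passes with probability 1 − (1 − 0.0116)^k: 11% for k = 10 and 21% for k = 20. The number screened is not stated; both values of k are assumptions.

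**Would the screen bring EGA back?** With 1:1 allocation within strata, and EGA assumed uniform over 23–33 weeks, EGA passed in 0–0.02% of simulated trials at n = 48 to 70. Without stratification it passed in about 1–4%.

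**The case against.** The strongest reply is that nothing fails. Planned power is met without the stratum, the test is either nominal or conservative, and no bias is expected in the linear models. The gain rests on an R² that the documents do not supply. All of this is true, and it limits the point to an available improvement.

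Second, the comparison above is with a bare two-group model, whereas the plan adjusts for PMA at assessment and later for medical risk, and uses a dyad random effect. Medical risk probably overlaps with immaturity. In a smaller simulation (6,000 trials per cell, Monte Carlo error about 0.5 point, assumed correlation 0.5 between medical risk and stratum), adding the stratum to a model with medical risk changed power by −0.5 to +0.5 point at R² 5–20% if medical risk carried at least half the stratum's effect. If it carried none, the gain was about 1, 2 and 4 points at R² 5, 10 and 20%. So the tabulated gains do not carry over to the second model. The first model is still exposed.

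Third, r may mean correlation with outcome. A noise factor would then pass with probability about 0.05 × 0.0116 = 0.06%, or about 1% of trials with 20 factors, and the rule would be partly prognostic. That stands as a reading. It still requires a chance imbalance before a prognostic factor can enter: a strongly prognostic one would pass only about 5% of the time.

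Fourth, the components of the social score are not listed, so the text does not show that it is measured after randomisation. That also stands.

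**Conclusion.** The concern holds as a worthwhile improvement and not a flaw that endangers the trial. The stratification factor is absent from every listed model, the listed covariates do not replace it, and the screen would almost never restore it.

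For the first model, the forgone power on the ASQ is about 1 point at R² 5%, 3 at 10%, and 5–7 at 20%. On the NNNS the change lies between about −1 and +3 points. These figures assume linear models and a standardised effect of 0.845, and they leave out dyad clustering and PMA adjustment. If allocation was balanced within strata, the test without the stratum is also conservative; if it was simple, it is not. Separately, the screen leaves undefined which covariates the reported treatment effect is adjusted for, whichever meaning of r was intended.

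**What to change.** - Put the EGA stratum, or EGA in weeks, into every outcome model as a fixed effect, starting with the first. State whether allocation was blocked within strata.
- Replace the p and r screen with a short list of covariates named on prognostic grounds. Report baseline differences descriptively only.
- Label any analysis adjusted for screened covariates as a sensitivity analysis. If the screen is kept for that purpose, define r and name the model it feeds.

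The document is dated April 2021 and written in the past tense, so the analyses may already have been run. In that case, report the stratum-adjusted model alongside the existing results and say that it was added later. Its covariate comes from the randomisation scheme and not from inspecting the data.

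The cost is a change of wording and one model term for a variable already held: one degree of freedom, and at most about 1 point of power if the stratum is not prognostic.
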